2.4 Subject Population

All patients from participating sites who are indicated for an atrial fibrillation ablation procedure and willing to provide written Informed Consent may be enrolled in this registry.

Point of Enrollment

Patients are considered enrolled in this registry following provision of written Patient Informed Consent.

Expected duration of each subject's participation

The expected duration of each subject's participation is 1 year.

Expected duration of the registry

The expected duration of this registry is approximately 3 years: 2 years of enrollment and 1 additional year of follow up.

Number of Patients required to be included in the registry

Up to 2,000 patients will be enrolled in this registry.

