One original signed consent document must be retained on file by the investigator and a second original signed consent document is provided to the subject (investigator's responsibility). The patient's legal rights will not be waived nor the appearance that these will be waived. Native non-technical language, understandable for the patient, will be used. Important new information that becomes available throughout the Registry will have to be provided in writing to new and existing patients. If relevant, all affected patients shall be asked to confirm their continuing informed consent in writing.

Baseline Visit

The following baseline information will be collected;

- Patient demographics
- Atrial fibrillation History (such as type, frequency, duration of atrial fibrillation and other arrhythmias other than AF),
- Cardiovascular history (NYHA class, LA diameter, LV EF% and degree of valvular heart disease),
- Cardiac medical history (pre-existing cardiac conditions and cardiac procedures).

Ablation procedure

- Devices used
- Ablation parameters
- Ablation success definition and result
- Operator feedback (Device combination chosen, device maneuverability, ease of use in combination with other device)
- Number, experience and type of attending personnel
- Definition of standard of care (follow-up procedures and occurrence)

6 and 12 Month Follow-up (+/- 30 days)

- Recurrence of atrial arrhythmias: list of atrial arrhythmias since last visit, classify episodes, duration of the episodes, (only events with source data evidence are to be recorded).
- Changes in therapy (new antiarrhythmic drug, redo procedures).
- In case of Repeat Ablation Procedures, reconnections and new ablations will be recorded.

Cardiovascular Serious Adverse Event

An adverse event is reportable in this registry when the event is deemed of cardiovascular origin and has the potential of leading to:

- Death
- A serious deterioration in the health of the subject, that can either result in:
 - o A life-threatening illness or injury OR
 - o A permanent impairment to a body structure or a body function OR
 - o An in-patient or prolonged hospitalization OR
 - o A medical or surgical intervention to prevent life-threatening illness or injury or permanent impairment to a body structure or a body function OR
 - o A malignant tumor
- Fetal distress, fetal death or a congenital abnormality or birth defect

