A planned hospitalization for a pre-existing condition is not considered a serious adverse event.

Potential Cardiovascular Serious Adverse Events (SAEs) include but are not limited to the following:

Abnormal ECG, Angina (chest pain), Arrhythmia, AV fistula, Complete heart block, Coronary artery injury, Cardiac perforation, Cardiac Thromboembolism, CHF exacerbation – fluid overload, Component damage to ICD or implantable pacemaker, Death, Dislodgement of implantable cardioverter defibrillator or permanent pacing lead, Endocarditis, Exacerbation of pre-existing atrial fibrillation, Heart Failure, Hypotension, Inadvertent AV block (complete heart block), Left atrial/esophageal fistula, Myocardial infarction, Obstruction/perforation/damage of the vascular system, Palpitation, Pericardial effusion/cardiac tamponade, Pericardial effusion without tamponade, Pericarditis, Pulmonary vein dissection, Pulmonary vein stenosis, Pulmonary vein thrombus, Temporary or complete heart block, Unintended (in)complete AV, sinus node, heart block/damage, Vessel wall/valvular damage or insufficiency and Ventricular arrhythmia requiring defibrillation.

Procedure for assessing, recording and reporting SAEs:

Cardiovascular SAEs must be reported following local regulation, no later than 7 days from site being made aware of the event. All cardiovascular SAEs between patient enrollment and end of registry must be reported to the sponsor and to the local ethics committees, as per local regulations.

Should an SAE occur, complete and submit an Adverse Event form to St. Jude Medical.

Additional information can be requested, if necessary, by the Sponsor for reporting of SAEs to regulatory authorities. The investigator must notify the Ethics Committee, if appropriate, in accordance with national and local laws and regulations.

Death

All patient deaths that occur during this registry must be reported to SJM within 72 hours of the center becoming aware of the death. An Adverse Event form should be completed for all deaths at all sites.

Protocol Deviations

Investigators are required to adhere to the study protocol, signed Investigator's Agreement, applicable federal (national) or state/local, laws and regulations, and any conditions required by the Ethics Committee or applicable regulatory authorities. A protocol deviation is used to describe situations in which the study protocol was not followed. All deviations from the study protocol must be reported to SJM.

Withdrawals

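### The exclusion of planned admissions from the SAE definition is not limited to conditions that have not worsened, so sites can classify some deteriorations either way and SAEs may be under-counted

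*Combined protocol and SAP*

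**What the plan says.** Section 3.2 (Cardiovascular Serious Adverse Event) makes an event reportable if it is cardiovascular and could lead to one of several outcomes. One of these is "A serious deterioration in the health of the subject, that can either result in" any of five things joined by OR, among them in-patient or prolonged hospitalization. That criterion does not separate planned from unplanned admissions.

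The exclusion follows directly: "A planned hospitalization for a pre-existing condition is not considered a serious adverse event". After it comes a list of potential cardiovascular SAEs. Some items on the list are, or can be, the worsening of a disease the patient already had: "Exacerbation of pre-existing atrial fibrillation" and "CHF exacerbation – fluid overload".

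The reporting window runs from enrollment to the end of the registry. Section 2.4 sets the population: "All patients from participating sites who are indicated for an atrial fibrillation ablation procedure and willing to provide written Informed Consent may be enrolled". AF is therefore pre-existing in every patient. The baseline visit also records NYHA class, ejection fraction, valvular disease and earlier cardiac conditions.

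Patient safety is the first objective in sections 2.2 and 6. Section 6 summarizes adverse events descriptively and also plans an analysis of physician experience against procedural outcomes or adverse events. It gives no expected SAE rate, safety threshold or safety test.

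**The concern.** The exclusion serves a sensible purpose: an elective admission for a stable, known condition should not be counted as harm. As written, however, it sets two conditions only, that the admission is planned and that the condition is pre-existing. Neither says that the condition must be no worse than at baseline, or that the planning must predate enrollment or the ablation. An admission scheduled months after the procedure, because a known cardiac condition has deteriorated, fits the exclusion. It also fits the deterioration criterion and may be named in the list.

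With about 100 centers, two defensible readings of one rule can put similar patients on different sides of the SAE count. The count feeds the first-listed objective. If admission practice differs between centers, part of any difference in SAE rates could reflect scheduling and not safety.

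**Working it through.** **Step 1. Is the limit supplied elsewhere?** The exclusion does not mention worsening, baseline status or time of planning. No other section defines planned or adds such a limit.

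**Step 2. Which cases are in conflict?** Reading the definition, the exclusion and the list together:

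| Case | Result under the text |
|---|---|
| New complication (for example tamponade, perforation, fistula, a valve damaged in the procedure) | Not pre-existing; the exclusion does not apply; reportable |
| Worsened pre-existing condition with another qualifying outcome (life-threatening, permanent impairment, intervention to prevent these) | Reportable through that outcome |
| Worsened pre-existing condition, only serious outcome an unplanned admission | Reportable; the exclusion does not apply |
| Worsened pre-existing condition, only serious outcome a planned admission | Either way |
| Unchanged pre-existing condition, planned admission | Excluded, as intended |

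Only the fourth row is in conflict. An example is a patient with baseline heart failure that worsens after the procedure, who is given a scheduled admission for fluid overload and meets no other criterion.

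**Step 3. Where does an excluded event go?** Table 1 has an SAE form but none for non-serious adverse events. For AF, the 6- and 12-month follow-up still captures recurrence, new antiarrhythmic drugs and redo procedures. For worsened heart failure or valve disease no other listed form applies, unless the patient dies or withdraws. Section 4.3 relies on central review of entered data, with on-site monitoring at the sponsor's discretion. An event that was never entered leaves little for central review to find.

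**Step 4. Direction and possible size.** The documents give no SAE rate and no share of planned admissions, so there is no figure to reproduce. Only N = 2,000 (an upper limit) comes from the plan. Two quantities are assumed: p, the true share of patients with a cardiovascular SAE, and s, the share of those patients left out under the exclusion.

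- Counted rate: o = p(1 − s)
- Patients missed: N × p × s
- 95% half-width: 1.96 × √(o(1 − o)/N), treating patients as independent

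For p = 5% and s = 20%: o = 0.05 × 0.80 = 4.0%; missed = 2,000 × 0.05 × 0.20 = 20; half-width = 1.96 × √(0.04 × 0.96/2,000) = 0.86 points.

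| p (assumed) | s (assumed) | Counted / true | Counted rate | Shortfall (points) | 95% half-width (points) |
|---|---|---|---|---|---|
| 3% | 0% | 60 / 60 | 3.0% | 0 | 0.75 |
| 3% | 10% | 54 / 60 | 2.7% | 0.30 | 0.71 |
| 3% | 20% | 48 / 60 | 2.4% | 0.60 | 0.67 |
| 3% | 30% | 42 / 60 | 2.1% | 0.90 | 0.63 |
| 5% | 0% | 100 / 100 | 5.0% | 0 | 0.96 |
| 5% | 10% | 90 / 100 | 4.5% | 0.50 | 0.91 |
| 5% | 20% | 80 / 100 | 4.0% | 1.00 | 0.86 |
| 5% | 30% | 70 / 100 | 3.5% | 1.50 | 0.81 |
| 10% | 0% | 200 / 200 | 10.0% | 0 | 1.31 |
| 10% | 10% | 180 / 200 | 9.0% | 1.00 | 1.25 |
| 10% | 20% | 160 / 200 | 8.0% | 2.00 | 1.19 |
| 10% | 30% | 140 / 200 | 7.0% | 3.00 | 1.12 |

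On this grid the shortfall exceeds sampling error only from s = 20% (p = 5% or 10%) or s = 30% (p = 3%).

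**Step 5. Contrast between sites.** Assume a true rate of 8% everywhere, that 30% of SAEs fall in the affected group, and that one set of sites schedules 60% of those admissions and another 20%. The rates read 0.08 × (1 − 0.3 × 0.6) = 6.56% and 0.08 × (1 − 0.3 × 0.2) = 7.52%, a spurious difference of 0.96 points. With an assumed 1,000 patients per set, the 95% half-width of the difference is 1.96 × √(0.0656 × 0.9344/1,000 + 0.0752 × 0.9248/1,000) = 2.2 points, so a contrast of this size would lie within sampling error.

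**The case against.** The strongest reply is that the exclusion speaks of a hospitalization and not of the event behind it. Reportability rests on what an event could lead to, and no actual admission is needed. On that reading a planned admission is not itself an SAE, while the deterioration that prompted it still is, and the list that follows confirms this by naming exacerbations. This is a reasonable reading and probably the intended one. It confines the problem to the fourth row in Step 2. It does not remove it, because the text does not require that reading and a site that omits such an event can cite a written rule.

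A second reply is that the data are collected elsewhere. That holds for AF recurrence and redo procedures, although they do not enter the SAE count. It does not hold for heart failure or valve disease.

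A third is that safety is summarized descriptively with no threshold, so no pass/fail conclusion can change. That stands, and it limits the consequence.

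A reader might infer more: that any listed event counts or not according to how the admission was booked, that procedural valve damage can escape, or that the SAE count is too low. The documents do not support this. Events with another qualifying outcome remain reportable. Valve damage in the procedure is a new and listed injury. Without an SAE rate or a share of planned admissions, an under-count is possible but not shown. Nor do the documents suggest that admission practice follows operator experience, so distortion of the learning-curve analysis is only a possibility.

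**Conclusion.** The point holds in a narrow form. The exclusion, the deterioration criterion and the event list in section 3.2 overlap, and nothing in the protocol settles the overlap. It affects pre-existing cardiac conditions that worsen after enrollment and whose only serious outcome is a planned admission.

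For these cases the rule can only remove events, so any bias in the cardiovascular SAE count is downward. Its size cannot be derived from the documents and may be zero. For assumed true rates of 3%, 5% and 10% and an assumed 0% to 30% left out, the number missed in 2,000 patients is 0 to 18, 0 to 30 and 0 to 60. These ranges show scale only and are not estimates.

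This is a cheap improvement to the measurement of the first-listed objective, not evidence that the safety result will be wrong.

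**What to change.** Keep the word planned and narrow the rule in section 3.2, for example:

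> A hospitalization for a pre-existing condition is not counted as an SAE if it was planned before enrollment, or if it was planned later without serious deterioration of the condition since baseline and not for a complication of the ablation.

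Keeping planned matters: without it, unplanned admissions for an unchanged condition could become excluded as well.

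State also that elective repeat ablation or cardioversion for recurrent AF, without other serious deterioration, is recorded as recurrence or on the Repeat procedure form. This is a reporting convention. An emergency admission for recurrent AF could still count while an elective one does not, and the report of results should say so.

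Add one field to the Adverse Event form: pre-existing condition worsened since baseline, yes/no. Reported SAEs that are worsened pre-existing disease can then be tabulated separately.

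The cost is a short change of wording and one form field, with no added visits or patients. The downside is a few more SAE forms and possibly a slightly less favourable SAE rate.

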3.2 Case Report Forms Content

Table 1: Data Collection

CRFs \ Visit	Enrollment & Baseline	Ablation Procedure	6 and 12 Months
Enrollment: Informed Consent Process	X		
Baseline: Demographics, Cardiovascular History, AF History, Medical History	X		
Ablation procedure		X	
Device user experience		X	
Follow Up Log*			X
Repeat procedure			(X)
Cardiovascular Serious Adverse Event	(X)	(X)	(X)
Withdrawal	(X)	(X)	(X)
Death	(X)	(X)	(X)

(X) if applicable

* Telephone or office visit

Enrollment & Informed Consent Process

The investigator is responsible for screening subjects for this registry and for obtaining patient informed consent, as applicable per local regulations. Provision of the Informed Consent is mandatory. Informed Consent is required from all patients (or their legal representatives) prior to participation in the investigation. The process of obtaining Informed consent shall comply with the most recent version of the declaration of Helsinki, ISO 14155 and all applicable regulations. The principal investigator or his/her authorized designee will conduct the Informed Consent Process. This process will include a verbal discussion with the patient on all aspects of the clinical investigation that are relevant to the patient's decision to participate in the clinical investigation. It is crucial that this discussion is documented in the source documents (read hospital records of the patient).

The patient will be provided with the informed consent form that is written in a language that is understandable to the patient and has been approved by Ethics Committee. The patient is given ample time to consider participation and ask questions if necessary.

In order to avoid any possible coercion or undue improper influence on, or inducement of the patient to participate, the Sponsor requests the investigator to only sign the informed consent form once the patient has signed and dated the document and therefore decided to participate in the investigation.

Informed Consent of a patient shall always be indicated by personally dated signature of the patient and by the investigator responsible for conducting the informed consent process. It is crucial that the signature of the informed consent is documented in the source documents (read hospital records of the patient).

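### Must the analysis section fix a time window for serious adverse events, given that reporting runs to the end of the registry but participation lasts one year?

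*Combined protocol and SAP*

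**What the plan says.** Section 3.2, under the procedure for SAEs, requires that "All cardiovascular SAEs between patient enrollment and end of registry must be reported to the sponsor", and also to ethics committees, subject to local rules. Section 2.4 defines the starting point: "Patients are considered enrolled in this registry following provision of written Patient Informed Consent". The same section says "The expected duration of each subject's participation is 1 year", and splits the registry's three or so years into "2 years of enrollment and 1 additional year of follow up".

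In Table 1 of Section 3.2, the row "Cardiovascular Serious Adverse Event" is marked, where applicable, under three headings: enrollment and baseline, the ablation procedure, and "6 and 12 Months". There is no later column. The two follow-up visits carry a tolerance of 30 days either way.

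Section 6 says that adverse events will be described and that categorical variables will be given as counts and proportions. Kaplan-Meier is offered as an option for arrhythmia recurrence only. For SAEs it names no time origin, window, denominator or censoring rule. No section says whether month 12 is counted from consent or from the procedure.

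**The concern.** Confirming patient safety is the first objective listed in Section 2.2. A proportion of patients with an SAE means little unless the reader knows over what period it was counted and from when. Read literally, the reporting sentence follows the first patient for three years and the last for one. Events after month 12 would reach the sponsor only if a site happened to learn of them, because no later contact is scheduled. One pooled proportion would then mix unequal exposure with incomplete capture and would exceed the 12-month risk by an unknown amount.

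Reporting also starts at consent, so events before ablation are collected, and patients who never reach ablation could sit in the denominator. Two analysts could both comply with Section 6 and publish different figures. The same events feed the learning-curve analysis.

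**Working it through.** **The plan's own figure.** 2 years of enrollment + 1 year of follow-up = 3 years, which agrees with Section 2.4.

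**Exposure under the two readings.** A patient enrolled at time *e* (0 to 2 years) has 3 − *e* years to the end of the registry: 3 for the first patient, 1 for the last. Assuming uniform enrollment, the mean is 2.0 years. For 2,000 patients (the ceiling in Section 2.4), that is 2,000 × 2.0 = 4,000 patient-years, against 2,000 × 1 = 2,000 on the one-year reading. Both ignore withdrawal and death.

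**Size of the late-event effect.** The documents give no SAE rate, so these inputs are assumptions: periprocedural risk *p* = 3%, later hazard *h* = 4% per year, and a share *c* of post-month-12 SAEs that reaches the database.

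- 12-month proportion: 1 − (1 − *p*)e^(−*h*) = 1 − 0.97 × 0.9608 = 6.80%.
- 95% half-width: 1.96 × √(0.068 × 0.932 / 2,000) = 1.10 points.
- Proportion to the end of the registry, averaged over uniform enrollment: 1 − (1 − *p*)e^(−*h*) × (1 − e^(−2*ch*)) / (2*ch*).

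| Late capture *c* | Proportion | Shift (points) | Extra patients of 2,000 |
|---|---|---|---|
| 0% | 6.80% | 0 | 0 |
| 10% | 7.18% | 0.37 | 7 |
| 25% | 7.73% | 0.93 | 19 |
| 50% | 8.64% | 1.84 | 37 |
| 100% | 10.43% | 3.63 | 73 |

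The shift equals the half-width at *c* of about 30%. Over *p* = 1% to 5% and *h* = 2% to 10% per year, it runs from 0.19 to 0.89 points at 10% capture and from 1.84 to 8.39 at 100%.

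**Time origin.** If ablation follows consent by 4 to 12 weeks (assumed) and the same 4% hazard applies, 1 − e^(−0.04 × 4/52) = 0.31% and 1 − e^(−0.04 × 12/52) = 0.92% of patients have an SAE before ablation, or 6 to 18 of 2,000. These events are listed separately once the summary is split by period.

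**Denominator.** If 2% to 10% of enrolled patients are never ablated (assumed), a 3.0% periprocedural risk reads 3.0 × 0.98 = 2.94% to 3.0 × 0.90 = 2.70%.

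**Visit tolerance.** Ending follow-up at month 11 or month 13 gives 1 − 0.97e^(−0.04 × 11/12) = 6.49% or 1 − 0.97e^(−0.04 × 13/12) = 7.11%.

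**Reading the sections together.** The long window appears only in the sentence on what sites must report. The analysis section does not adopt it. It also does not set the analysis origin at consent; it leaves the origin open. The schedule for the SAE form ends at month 12, as does each patient's expected participation. Table 1's three headings already separate events before ablation, at the procedure and during follow-up.

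**The case for a change.** The strongest case for a change is that Section 2.4 gives the subject and the registry different durations, one year and about three. Section 3.2 uses the registry's term for SAEs and again for deaths, so the literal reading is not far-fetched. Full capture of late events would move the illustrative figure by more than three half-widths (3.63 / 1.10 = 3.3). Even on the one-year reading, Section 6 lacks an origin, a denominator and a rule for withdrawals. A few sentences would settle it.

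What stands is that these details are unwritten and that the reporting sentence sits awkwardly beside Table 1. The rest is weaker. The large shifts need near-complete capture after month 12, and no contact is scheduled then. A procedure-anchored summary remains open under Section 6. For the learning curve, "Number, experience and type of attending personnel" are recorded at the procedure and the method is left open, so a bias there is only a possibility.

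A tight rule has its own difficulty. If month 12 runs from consent, a wait of 4 to 12 weeks puts the last scheduled contact 48 to 40 weeks after ablation (52 − 4 and 52 − 12). A fixed day-365 window from the procedure would then outrun scheduled follow-up for many patients. Kaplan-Meier for SAEs and a day-30 cut are reasonable preferences, but this plan does not have to adopt them.

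**Conclusion.** The gap is real, but no change to the plan is needed. Collecting SAEs broadly, from consent for as long as the registry is open, is ordinary post-market practice and differs from choosing what to tabulate. No stated rule or number in the plan is shown to give a wrong result. An analyst would take Table 1 as the guide: report SAEs at the procedure and through the 12-month visit among ablated patients, list earlier and later events apart, and state the period beside each proportion. The forms should support this, provided the Adverse Event form records an onset date (its fields are not listed in the protocol).

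The size of any effect is unknown. It is zero for late exposure if capture ends at month 12, the likelier reading. Under the assumed 3% and 4% per year, it stays within the 1.10-point half-width until about 30% of late events are captured. The study is single-arm and descriptive, with no stated hypothesis test or safety threshold, so no error rate or power calculation is affected.
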